## **2.5 Potential Risks and Benefits**

### **2.5.1 Potential Risks**

It is anticipated that subjects participating in the study will be exposed to the same risks as those associated with AV graft implantation (some of which have been reported in Phase 2 trial with the HAV – see Investigator Brochure). Risks associated with the HAV may include, but are not limited to, the following:

- Aneurysm or pseudo-aneurysm formation
- HAV rupture
- Bleeding and hematoma formation at the surgical site or the dialysis puncture sites
- Thrombosis/occlusion of the HAV or host vessels

- Stenosis of the HAV or its anastomoses
- Infection of the HAV, at the surgical site or a systemic infection
- Skin erosion
- Steal syndrome and/or high output cardiac failure
- Swelling of the limb

The risks anticipated in this study are similar to those associated with currently marketed prosthetic grafts used for dialysis access. There has been 1 reported aneurysmal dilatation of the HAV in Phase 2. The superficial site of implantation of the HAV facilitates clinical and regular ultrasound monitoring, allowing any such complication to be recognized and treated promptly, and thus minimizing potential risk to the subject.

The HAV is grown using donor human aortic smooth muscle cells. The HAV is decellularized during manufacturing and thus consists of only human ECM proteins. It is possible that the HAV may provoke an immune response which may lead to damage of the HAV and possible cross reactivity against host proteins. Antibody formation will be assessed by monitoring of PRA levels.

### **2.5.2 Potential Benefits**

Subjects who undergo implantation of the Humacyte HAV may benefit from reduced infections and improved patency, which may translate into a reduced number of interventions versus a conventional ePTFE graft. Based on the known biology of the HAV, the HAV has the potential to offer a reduced risk of infection and less intimal hyperplasia, which could offer a longer period of use (i.e., delayed abandonment).

### **3. STUDY OBJECTIVES**

#### **3.1 Primary Objective**

To evaluate the safety, efficacy and immunogenicity over 3 months after implantation of HAVs manufactured using the commercial manufacturing system (Luna).

#### **3.2 Secondary Objective**

To evaluate the long-term safety and efficacy of the HAV (manufactured with the Luna system) over a period of up to 36 months after implantation.

## 4. STUDY DESIGN

### 4.1 Description of the Study Design

This is a Phase 2, prospective, multicenter, open-label, single-arm study. Subjects who sign informed consent would undergo study-specific screening assessments within 45 days from the day of informed consent.

Eligible study subjects will receive a HAV and will be followed to 12 months post-implantation at routine study visits regardless of patency status. After 12 months, subjects with a patent HAV will be followed (while the HAV remains patent) for up to 3 years (36 months) post-implantation at study visits every 6 months.

### 4.2 Study Endpoints

#### 4.2.1 Safety Endpoints

##### 4.2.1.1 Primary Safety Endpoints – assessed at 3 months post implantation

- Adverse events indicating possible mechanical failure or weakness of the HAV
  - Anastomotic rupture
  - Anastomotic bleeding
  - Spontaneous HAV rupture
  - Aneurysm
  - Pseudoaneurysm
  - Abnormal post cannulation hemostasis
- HAV infections
- Change from baseline of PRA and anti-HAV IgG levels (at 2 months)
- All AEs/SAEs and adverse events of special interest.

##### 4.2.1.2 Secondary Safety Endpoints – assessed throughout the 36 month post implantation follow-up

- Adverse events indicating possible mechanical failure or weakness of the HAV
  - Anastomotic rupture
  - Anastomotic bleeding
  - Spontaneous HAV rupture
  - Aneurysm
  - Pseudoaneurysm
  - Abnormal post cannulation hemostasis
- HAV infections
- Change from baseline of PRA and anti-HAV IgG levels (at 12 months)

- All AEs/SAEs until 12 months post implant, after that only SAEs associated with the HAV and adverse events of special interest.

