#### **2.3.2.1 CLN-PRO-V001 and CLN-PRO-V003 Study Results (24 M)**

All subjects (n = 60) have now completed at least 24 months since implantation (or had a censoring event). The first subjects recruited are now beyond 60 months after HAV implantation, some with functioning HAV for hemodialysis access. Together these 2 trials provide more than 150 years of follow up during which the HAV has been used for more than 15,000 hemodialysis sessions.

When HAV thrombosis has occurred it has almost always been managed successfully, often allowing immediate resumption of dialysis without the need for the placement of a dialysis catheter. One non-serious arteriovenous graft aneurysm was reported in Study CLN-PRO-V001 (moderate in intensity, considered possibly related to IMP and considered not related to procedure – this patient died before the Sponsor could complete the follow up of this event). An expected number of small pseudoaneurysms have been observed, which is consistent with all surgically-created hemodialysis access. Most have resolved spontaneously with only 2 cases requiring surgical intervention. Flow rates through the HAV were more than sufficient to allow for effective dialysis.

In both studies, the product has generally been well tolerated and blood chemistry, hematology and coagulation data are not indicative of any HAV-associated toxicity. Immunogenic response to the HAV material has not been observed as demonstrated by a general lack of HAV-related change in PRA levels (Class I or II). Three subjects had elevations in their PRA levels: all 3 subjects had experienced 1 or more renal transplant failures; 1 subject recently; 1 subject developed septic shock about a month before the elevated value; and the third subject, who

was severely debilitated with a decubitus ulcer, died approximately a month after HAV abandonment.

IgG titers increased in 5 subjects; in 4 cases the IgG titer increased and then decreased while the HAV remained functional with no clinical evidence of an inflammatory response; in 1 case the IgG titer increase occurred in a subject who maintained primary patency.

Adverse events (AEs) related to the HAV/access site (excluding thrombotic events) were few; there have been only 3 access-site infections, of which only 1 required removal of part of the HAV. There have been:

- 1 kidney transplant (known to be functioning well at 12 months post-transplant)

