- 15 deaths, all after abandonment or during follow-up; none of the deaths were considered related to the presence of the HAV

Patency data for the 2 studies in dialysis access has been pooled for a combined Kaplan-Meier (K-M) analysis ([Lawson, 2016](#)). Based on these K-M plots the patency at 6, 12 and 24 months is estimated to be 60%, 26% and 15% (primary patency) and 97%, 91% and 77% (secondary patency).

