## 9. SAFETY ASSESSMENTS AND ADVERSE EVENTS

The safety of the HAV will be assessed in terms of the following:

- Anastomotic rupture
- Anastomotic bleeding
- HAV spontaneous rupture
- Aneurysm
- Pseudoaneurysm
- HAV infection
- Increase from baseline in PRA/Anti-HAV IgG antibodies
- Need for HAV revision or removal
- Other AEs
- Laboratory parameters (clinical chemistry and hematology)

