### **9.3 Events of Special Interest**

Events of Special Interest related to interventions and infections will be evaluated and include the following:

- Events resulting in HAV abandonment
- HAV thrombosis
- HAV infection
- HAV aneurysm (HAV lumen diameter > 9 mm ) formation
- Clinically significant HAV pseudoaneurysm (clinically significant defined as requiring a surgical or radiological intervention)
- HAV spontaneous rupture
  - Iatrogenic injuries are not an Event of Special Interest and should be reported as an AE
- Events resulting in HAV revision or ligation

- Events resulting in HAV removal
- Clinically significant stenosis of HAV (clinically significant defined as severity of severe or greater, or requiring a surgical or radiological intervention)
- Clinically significant Steal Syndrome (clinically significant defined as severity of severe or greater, or requiring a surgical or radiological intervention)
- Anastomotic bleeding
- Anastomotic rupture

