## 9.6 Reporting of Adverse Events

At each evaluation, the subject will be questioned in a general way and no specific symptoms will be suggested. If any AEs have occurred, they will be recorded on the AE pages of the eCRF and in the subject's medical record. If known, the diagnosis should be recorded in preference to the listing of individual signs and symptoms.

During the Screening period (Day -45 to Day 0 prior to implantation), only SAEs related to study procedures will be reported beginning at the time the subject signs the informed consent form. From Day 0 after implantation to 1 year post-implantation (Month 12 visit) or ET visit, whichever occurs earlier, all AEs will be reported.

During the long-term follow-up period from 1 year to 3 years post-implantation, only the following will be reported by the investigator:

- All related SAEs
- All Events of Special Interest (as defined in [Section 9.3](#)).

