3: If adequate vessel mapping has been undertaken within the 8 weeks prior to the start of Screening and there has been no significant change in the condition of the subject (including insertion of CVC) then repeat vessel mapping is at the discretion of the Principal Investigator. Vessel mapping performed by ultrasound in the clinic by the investigator is acceptable.

4: After review by the Principal Investigator, the subject's Screening eCRFs will be provided to the Medical Monitor for review and confirmation of eligibility prior to implantation.

5: Labs include hematology and chemistry. Screening labs will also include INR (or PT if INR value not available) and a serum or urine pregnancy dipstick test for women of childbearing potential. Standard of care laboratory evaluations conducted prior to consent may be used for determination of eligibility provided they are within the screening period time window.

6: Intraoperatively or immediately post-surgery and at Day 7-15, the investigator should use his/her preferred method to confirm patency and adequate flow in the HAV. At all other timepoints, duplex ultrasound will be used to assess patency, diameter of the lumen mid-conduit and flow rate and to monitor aneurysm development. After Month 12, a duplex ultrasound is to be performed at Month 24 and 36.

7: Beginning on Day 28, the investigator may evaluate the HAV to determine if it is suitable to be used for dialysis.

8: Only SAEs related to the screening procedures will be reported during the Screening period. All AEs will be reported from Day 0 after implantation up to the Month 12 visit. After the Month 12 visit up to Month 36, only the following will be reported by the investigator:

- All SAEs considered related to the HAV
- All Events of Special Interest.

9: Subjects will be assessed at a study visit that can occur anytime from Day 7 to 15.

10: Subjects withdrawn prior to the Month 36 visit will have ET assessments performed. Patients withdrawn prior to Month 12 should complete an ET that correlates with the procedures at Month 12. Patients withdrawn after Month 12 and prior to Month 36 should complete an ET visit that correlates with procedures post Month 12 through Month 36.

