## **2.2.2 Secondary Endpoints**

### **2.2.2.1 Secondary Safety Endpoints – assessed throughout the 36 months post implantation follow-up**

- Adverse events indicating possible mechanical failure or weakness of the HAV
  - Anastomotic rupture
  - Anastomotic bleeding
  - Spontaneous HAV rupture
  - Aneurysm
  - Pseudoaneurysm
  - Abnormal post cannulation hemostasis
- HAV infections
- Change from baseline of PRA and anti-HAV IgG levels (at 12 months)
- All AEs/SAEs until 12 months post implant, after that only SAEs associated with the HAV and adverse events of special interest.

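### The 36-month adverse event tables would pool full and narrowed reporting for pseudoaneurysm and abnormal post-cannulation hemostasis; a Month 12 split in the SAP resolves it

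*Protocol*

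**What the plan says.** **Endpoints.** Protocol 4.2.1.2 is headed "Secondary Safety Endpoints – assessed throughout the 36 month post implantation follow-up", and SAP 2.2.2.1 "Secondary Safety Endpoints – assessed throughout the 36 months post implantation follow-up". Under adverse events that may indicate mechanical failure or weakness of the vessel, both name pseudoaneurysm and abnormal post-cannulation hemostasis, neither with a severity limit. The last bullet of each list covers all adverse events to 12 months, and after that only serious events associated with the vessel and events of special interest.

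**Reporting.** Protocol 9.6 reports all adverse events up to the Month 12 visit. It then says: "During the long-term follow-up period from 1 year to 3 years post-implantation, only the following will be reported by the investigator", namely related serious adverse events and Events of Special Interest. Appendix 1 note 8 agrees ("After the Month 12 visit up to Month 36, only the following will be reported by the investigator"), as does SAP 7.2.

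**Events of Special Interest.** Protocol 9.3 admits pseudoaneurysm only in this form: "Clinically significant HAV pseudoaneurysm (clinically significant defined as requiring a surgical or radiological intervention". Abnormal post-cannulation hemostasis is not on the list.

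**Analysis.** SAP 7.2.5 counts subjects with any treatment-emergent event by system organ class and preferred term, with no split by period. SAP 7.2.6 gives a pseudo-aneurysm rate over all vessel exposure and notes that only clinically significant cases go on being recorded from year 1 to year 3. It has no line for abnormal hemostasis. SAP 6.2 does split intervention rates into Day 0 to Month 12 and overall.

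**The concern.** Two of the protocol's own indicators of mechanical weakness are declared as 36-month endpoints, while the rule for reporting them changes at Month 12. Protocol 2.4 gives long-term safety of the Luna product as the reason for following patients with a patent vessel to 36 months. In a table pooled over 36 months, a low count of late pseudoaneurysm or abnormal hemostasis could reflect the vessel's behavior or the narrower reporting, and the table could not show which.

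The protocol's own experience makes this plausible for pseudoaneurysm. Of the cases in the two earlier dialysis studies, Protocol 2.3.2.1 says: "Most have resolved spontaneously with only 2 cases requiring surgical intervention". Cases that resolve without intervention are the ones that leave the reporting net after Month 12, unless they are related and serious.

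**Working it through.** **1. The passages side by side**

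| Event | Day 0 to Month 12 | After Month 12 |
|---|---|---|
| Pseudoaneurysm needing intervention | reported | reported (special interest) |
| Pseudoaneurysm without intervention | reported | only if a related serious event |
| Abnormal post-cannulation hemostasis | reported | only if a related serious event, or if it leads to a listed event such as revision or abandonment |
| Rupture, anastomotic bleeding, aneurysm | reported | reported (special interest) |

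The gap is therefore partial for pseudoaneurysm and wider for hemostasis. The plan states no figure on this point, so there is none to reproduce.

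**2. How much exposure lies on each side of Month 12**

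Inputs from the documents: up to 30 subjects; secondary patency of 97%, 91% and 77% at 6, 12 and 24 months (Protocol 2.3.2.1). Assumption: 65% at 36 months. S(t) is linear between these points.

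- Year 1, per subject: 0.5 × (1 + 0.97)/2 + 0.5 × (0.97 + 0.91)/2 = 0.9625 years; × 30 = 28.9.
- Years 2 and 3, per subject: (0.91 + 0.77)/2 + (0.77 + 0.65)/2 = 1.55 years; × 30 = 46.5.
- Share after Month 12: 46.5 / 75.4 = 62%. With 36-month patency of 50% to 77% and 0 to 20% yearly loss to death or transplant, the share is 53% to 63%.

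**3. Illustrative under-count in the pooled table**

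Assumptions, none from the documents: l = event hazard per patent-year in year 1; h = ratio of late to early hazard; c = share of late events still reportable.

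- Early subjects: E = 30 ∫₀¹ l·exp(−l·t)·S(t) dt
- True late subjects: L = 30·exp(−l) ∫₁³ h·l·exp(−h·l·(t−1))·S(t) dt
- Recorded late subjects R: the same as L with c·h·l in place of h·l
- Missed: L − R

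With l = 0.10 and no deaths or transplants, E = 2.75 subjects (9.2% of 30):

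| h | True total E + L | Missed, c = 0 | Missed, c = 0.25 | Missed, c = 0.5 |
|---|---|---|---|---|
| 1 | 6.58 (21.9%) | 3.83 | 2.81 | 1.83 |
| 0.5 | 4.76 (15.9%) | 2.01 | 1.49 | 0.98 |
| 0.25 | 3.78 (12.6%) | 1.03 | 0.77 | 0.51 |

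The earlier studies had 15 deaths in more than 150 years of follow-up, about 0.10 per year. With that loss rate the top-left figure falls from 3.83 to about 3.2.

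Full grid: l = 0.05, 0.10, 0.20; h = 1, 0.5, 0.25; c = 0, 0.25, 0.5; 36-month patency 0.50, 0.65, 0.77; yearly loss 0, 10, 15, 20%. That is 3 × 3 × 3 × 3 × 4 = 324 combinations. Missed subjects run from about 0.2 to 6.6, with a median of about 1.1. As a share of subjects with an event, the range is about 10% to 61%.

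**4. The 12-month analysis**

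If enrollment is even over the stated 2 months, a subject has on average 1 month past Month 12 when the last subject reaches it. That is about 0.083 × 0.90 = 0.075 patent-years, and 0.075 / (0.9625 + 0.075) = 7.2%. Over 1 month of enrollment it is 3.8%. With yearly loss up to 20% these fall to about 6.4% and 3.4%.

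**The case against.** **The narrowing is stated in the endpoint list itself.** The mechanical-failure bullet is about adverse events, so the last bullet can be read as governing it too. This is a fair reading and it reduces the point from a contradiction to an ambiguity. It does not settle it: the last bullet qualifies the line on all adverse events, and the mechanical-failure bullet stands apart without a limit.

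**A 12-month cut is already planned.** SAP 4 schedules that analysis, and Protocol 12 describes an addendum with data up to 12 months. This stands. A reader might infer that the two reporting periods can be separated only by rebuilding the split from the onset-dated listings. The documents do not support that: the 12-month tables come close to a full-reporting cut. What remains is that the 36-month tables are pooled.

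**Abnormal hemostasis is not left out of the plan.** Protocol 9, under "The safety of the HAV will be assessed in terms of the following", includes a category for other adverse events, and SAP 7.2.5 would tabulate the event by preferred term. This stands; the event lacks only a line of its own in SAP 7.2.6.

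**Other records exist.** Late visits include access-site examination, documentation of access problems, and duplex ultrasound (Protocol 8.6.1.2, 8.6.1.4, 8.6.1.7; Appendix 1 note 6). SAP 7.7 lists such data and summarizes them where deemed appropriate. These may hold some late cases, and the case report form cannot be seen. The SAP does not link them to either endpoint.

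**The pseudo-aneurysm rate.** A reader might infer that the SAP 7.2.6 rate is diluted by the 53% to 63% of exposure after Month 12. Its natural reading is clinically significant events only, which stay reportable to Month 36, and then it has no such bias.

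**The illustration is driven by assumptions.** This stands. The upper end of 6.6 needs a hazard of 0.20 unchanged after year 1, no late capture, no deaths or transplants, and no patency loss after Month 24. Zero late capture cannot apply to pseudoaneurysm, because intervention cases remain reportable.

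**Conclusion.** The mismatch between endpoint scope and late reporting is in the text, subject to the ambiguity of the last endpoint bullet. If the plan is followed as written, the 36-month tables under SAP 7.2.5 combine a period of full reporting with a period of narrowed reporting for these two events. Late non-serious cases without intervention would be under-counted in those tables.

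The size cannot be known from the documents. About 1 subject of 30 is the median of the assumptions tried, within a range of about 0.2 to 6.6. That median describes the chosen grid and is not an estimate. It would be wrong to infer that the late count is known to be seriously biased, or that important late failures would go unseen: rupture, anastomotic bleeding, aneurysm, pseudoaneurysm needing intervention, and events leading to revision, removal or abandonment all stay reportable.

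The weight is minor. The endpoints are secondary and descriptive, with no hypothesis test. The 3-month analysis is unaffected and the 12-month analysis barely so.

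**What to change.** In the SAP:

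1. In the final analysis, summarize pseudoaneurysm of any severity and abnormal post-cannulation hemostasis on events and exposure from Day 0 to Month 12, with the split that SAP 6.2 already applies to interventions. Because full reporting runs to the Month 12 visit, the SAP should say whether the cut is that visit or a fixed day.
2. To Month 36, report only clinically significant pseudoaneurysm, the other Events of Special Interest and related serious adverse events. State that the SAP 7.2.6 pseudo-aneurysm rate counts clinically significant events only.
3. Footnote the 36-month adverse event tables to say that reporting narrows after Month 12.

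The cost is one extra data cut, using onset dates already in the planned listing, and no new data. The downside is a narrower stated scope for the late endpoint: late cases that are neither related serious events nor Events of Special Interest fall outside it. These SAP changes need no protocol amendment.

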## 4.2.2 Efficacy Endpoints

### 4.2.2.1 Primary Efficacy Endpoints – assessed at 3 months post implantation

- Primary patency
  - Defined as being maintained until any intervention designed to maintain or reestablish patency, access thrombosis or the measurement of patency', i.e., patent without interventions
- Primary assisted patency
  - Defined as being maintained until access thrombosis or the time of measurement of patency, including intervening manipulations (surgical or endovascular interventions) designed to maintain the functionality of patent access' i.e., patent without an intervention to clear a thrombus
- Secondary patency
  - Defined as being maintained until access abandonment
  - Access abandonment defined as no remaining segment of the study conduit is incorporated into the vascular access circuit used for dialysis

### 4.2.2.2 Secondary Efficacy Endpoints – assessed throughout the 36 month post implantation follow-up

- Primary patency
- Primary assisted patency
- Secondary patency
- Interventions required to achieve/maintain secondary patency.
- Histopathological remodeling of any HAV (based on any samples collected).

## 4.3 Duration of Study Participation

Each subject will be followed at study specific visits until he/she has completed 12 months of follow-up after implantation (irrespective of patency status). After 12 months, subjects with a patent HAV will be followed (while the HAV remains patent) for up to 3 years (36 months) post-implantation at study visits every 6 months.

The expected duration of the clinical investigation is 40 months (initiation of enrollment through completion of data collection).

## 5. STUDY POPULATION

### 5.1 Description of the Study Population

The study population will consist of subjects with ESRD who require hemodialysis and are targeted for implantation of an AV graft for dialysis access.

#### 5.1.1 Inclusion Criteria

1. Subjects with ESRD who are not, or who are no longer candidates for creation of an autologous AV fistula and therefore need placement of an AV graft in the arm (upper- or forearm) for hemodialysis therapy.
2. Already established on hemodialysis
3. At least 18 years of age at Screening.
4. Suitable arterial and venous anatomy for implantation of straight or looped conduits in either the forearm or upper arm (not crossing the elbow).
5. Hemoglobin  $\geq$  8 g/dL and platelet count  $\geq$  100,000 cells/mm^3 prior to Day 0 (within 45 days).
6. Other hematological and biochemical parameters within a range consistent with ESRD prior to Day 0 (within 45 days).
7. Normal clotting (international normalized ration [INR]  $\leq$  1.5 or prothrombin time  $\leq$  18 sec unless the patient is taking an anticoagulant for an approved indication at the time of HAV implantation).
8. Female subjects must be either:
  - a. Of non-childbearing potential, which is defined as post-menopausal (at least 1 year without menses prior to Screening) or documented surgically sterile or post hysterectomy (at least 1 month prior to Screening)
  - b. Or, of childbearing potential, in which case:
    - i. Must have a negative serum or urine pregnancy test at Screening, and
    - ii. Must agree to use at least one form of the following birth control methods for the duration of the study:
      1. Established use of oral, injectable or implanted hormonal methods of contraception
      2. Placement of an intrauterine device or intrauterine system
      3. Barrier methods of contraception: condom or occlusive cap (diaphragm or cervical/vault caps) with spermicidal foam/gel/film/cream/suppository

9. Subject, or legal representative, able to communicate effectively with investigative staff, competent and willing to give written informed consent, and able to comply with entire study procedures including all scheduled follow-up visits.
10. Life expectancy of at least 1 year.

